**Table A 30. GCRS responses over time for subjects randomized to Restylane Defyne, Blinded Evaluator (FAS)**

Time point	GCRS								Total N	
	0 No Retrusion		1 Mild Retrusion		2 Moderate Retrusion		3 Severe Retrusion			
	n	%	n	%	n	%	n	%		
Baseline/initial treatment	xx	xx.x	xx	xx.x	xx	xx.x	xx	xx.x	xx	
3M after last treatment	xx	xx.x	xx	xx.x	xx	xx.x	xx	xx.x	xx	
6M after last treatment	xx	xx.x	xx	xx.x	xx	xx.x	xx	xx.x	xx	
9M after last treatment	xx	xx.x	xx	xx.x	xx	xx.x	xx	xx.x	xx	
12M after last treatment	xx	xx.x	xx	xx.x	xx	xx.x	xx	xx.x	xx	

% = (n/N)*100

Table A 31. GCRS responses over time for subjects randomized to Control Group, Blinded Evaluator (FAS)

Time point	GCRS								Total N	
	0 No Retrusion		1 Mild Retrusion		2 Moderate Retrusion		3 Severe Retrusion			
	n	%	n	%	n	%	n	%		
Baseline/randomization	xx	xx.x	xx	xx.x	xx	xx.x	xx	xx.x	xx	
3M after randomization	xx	xx.x	xx	xx.x	xx	xx.x	xx	xx.x	xx	
6M after randomization/treatment	xx	xx.x	xx	xx.x	xx	xx.x	xx	xx.x	xx	
3M after last treatment	xx	xx.x	xx	xx.x	xx	xx.x	xx	xx.x	xx	
6M after last treatment	xx	xx.x	xx	xx.x	xx	xx.x	xx	xx.x	xx	
9M after last treatment	xx	xx.x	xx	xx.x	xx	xx.x	xx	xx.x	xx	
12M after last treatment	xx	xx.x	xx	xx.x	xx	xx.x	xx	xx.x	xx	

% = (n/N)*100

Table A 32. GCRS responses over time for subjects randomized to Restylane Defyne, Treating Investigator (FAS)

Same as table A 30

[figure not shown]
$\% = (n/N)*100$

Table A 33. GCRS responses over time for subjects randomized to Control Group, Treating Investigator (FAS)

Same as table A 31

$\% = (n/N)*100$

CCI

A large black rectangular redaction box covers the majority of the page content below the CCI label, starting from the 'CCI' text and extending down to the bottom of the page.

Title

Statistical Analysis Plan 43CH1627 - Chin

Doc id

MA-38115

CCI

Title

Statistical Analysis Plan 43CH1627 - Chin

Doc id

MA-38115

CCI

Page 31 of 41

Version: 1.0

Effective

Effective date: 2018-08-23 03:02

Title

Statistical Analysis Plan 43CH1627 - Chin

Doc id

MA-38115

CCI

Page 32 of 41

Version: 1.0

Effective

Effective date: 2018-08-23 03:02

**Table A 39. Exposure to study treatment (Safety)**

Assessment	Parameter	Restylane Defyne N=xx	Control (optional treatment) N=xx	Total N=xx
Volume of injection(mL) for treatment	N	xx	xx	xx
	Mean (SD)	x.xx (x.xx)	x.xx (x.xx)	x.xx (x.xx)
	Median	x.x	x.x	x.x
	Min, Max	x.x, x.x	x.x, x.x	x.x, x.x
Volume of injection(mL) for touch-up	N	xx	xx	xx
	Mean (SD)	x.xx (x.xx)	x.xx (x.xx)	x.xx (x.xx)
	Median	x.x	x.x	x.x
	Min, Max	x.x, x.x	x.x, x.x	x.x, x.x
Total volume of injection (mL) for treatment+touch-up	N	xx	xx	xx
	Mean (SD)	x.xx (x.xx)	x.xx (x.xx)	x.xx (x.xx)
	Median	x.x	x.x	x.x
	Min, Max	x.x, x.x	x.x, x.x	x.x, x.x
Depth of injection for treatment	n (%)	xx (xx.x%)	xx (xx.x%)	xx (xx.x%)
Mid to deep dermis				
Subcutaneous	n (%)	xx (xx.x%)	xx (xx.x%)	xx (xx.x%)
Supraperiosteal	n (%)	xx (xx.x%)	xx (xx.x%)	xx (xx.x%)
Other	n (%)	xx (xx.x%)	xx (xx.x%)	xx (xx.x%)
Depth of injection for touch-up	n (%)	xx (xx.x%)	xx (xx.x%)	xx (xx.x%)
Mid to deep dermis				
Subcutaneous	n (%)	xx (xx.x%)	xx (xx.x%)	xx (xx.x%)
Supraperiosteal	n (%)	xx (xx.x%)	xx (xx.x%)	xx (xx.x%)
Other	n (%)	xx (xx.x%)	xx (xx.x%)	xx (xx.x%)
Method of injection for treatment	n (%)			
.	n (%)			
.	n (%)			
.	n (%)			
Method of injection for touch-up	n (%)			
.	n (%)			

% = 100*n/N

**Table A 40. Treatment procedure (Safety)**

Time point	Assessment	Parameter	Restylane N=xx	Control N=xx	Total N=xx
Treatment	Local anesthesia used?	Yes	n (%)	xx (xx.x%)	xx (xx.x%)
		No	n (%)	xx (xx.x%)	xx (xx.x%)
	Whereof topical cream	n (%)	xx (xx.x%)	xx (xx.x%)	xx (xx.x%)
	Whereof local infiltration	n (%)	xx (xx.x%)	xx (xx.x%)	xx (xx.x%)
Touch-up	Local anesthesia used?	Yes	n (%)	xx (xx.x%)	xx (xx.x%)
		No	n (%)	xx (xx.x%)	xx (xx.x%)
	Whereof topical cream	n (%)	xx (xx.x%)	xx (xx.x%)	xx (xx.x%)
	Whereof local infiltration	n (%)	xx (xx.x%)	xx (xx.x%)	xx (xx.x%)
Treatment	Post-treatment care	None	n (%)	xx (xx.x%)	xx (xx.x%)
		Massage	n (%)	xx (xx.x%)	xx (xx.x%)
		Ice pack	n (%)	xx (xx.x%)	xx (xx.x%)
		No	n (%)	xx (xx.x%)	xx (xx.x%)
Touch-up	Post-treatment care	None	n (%)	xx (xx.x%)	xx (xx.x%)
		Massage	n (%)	xx (xx.x%)	xx (xx.x%)
		Ice pack	n (%)	xx (xx.x%)	xx (xx.x%)
		Other	n (%)	xx (xx.x%)	xx (xx.x%)

% = 100*n/N

**Table A 41. A brief summary of all AEs (Safety)**

	No treatment at baseline N=xx			Treatment with Restylane Defyne N=xx		
	Subjects		Events	Subjects		Events
	n	%	#	n	%	#
Any AEs reported, total	xx	xx.x	xx	xx	xx.x	xx
Of which were serious	xx	xx.x	xx	xx	xx.x	xx
AEs related to product and/or injection procedure	xx	xx.x	xx	xx	xx.x	xx
Of which were serious	xx	xx.x	xx	xx	xx.x	xx
AEs unrelated to product and/or injection procedure	xx	xx.x	xx	xx	xx.x	xx
Of which were serious	xx	xx.x	xx	xx	xx.x	xx
Subjects with no AE reported	xx	xx.x	-	xx	xx.x	-

Note: Treatment with Restylane Defyne columns include data from subjects in the Restylane Defyne group after their initial treatment at baseline, as well as data from subjects in the Control group after their initial treatment at Month 6 after randomization

% = 100*n/N

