3.1 Objective of the study

- To evaluate the effectiveness and safety of Restylane Defyne versus a no-treatment control in the treatment of Chin Retrusion.

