4.1 General Outline

This is a randomized, evaluator-blinded, no-treatment controlled study in subjects with Chin Retrusion.

Subjects will be screened for eligibility within 21 days prior to Baseline. Eligible subjects will be randomized either to the Treatment Group or the Control Group in a 3:1 ratio.

| | | |
|--|--|---------------------------|
|  GALDERMA | Title 43CH1627 Clinical Study Protocol | Doc id MA-34970 |
|--|--|---------------------------|

Effective date: 2018-01-15 10:39

Effective

Version: 3.0

Treatment

Each subject assigned to the Treatment Group will receive an initial treatment on Day 1. A touch-up treatment may be performed 4 weeks after the initial treatment if optimal chin augmentation has not been obtained. Optimal chin augmentation is defined as the best possible aesthetic result that can be obtained for an individual study participant, as agreed upon by the Treating Investigator and subject. At least one (≥ 1) grade improvement from baseline on the GCRS should be the treatment target.

Subjects assigned to the Control Group will not receive treatment at baseline but will return for routine follow-up. At month 6 visit after randomization, subjects in Control Group will be offered a treatment and, at the following visit, an optional touch-up treatment.

Evaluation of effectiveness

Chin Retrusion will be assessed using a separate Four-Point GCRS with photo guides by the Treating Investigator at each visit; and by the Blinded Evaluator at screening, baseline, 3, 6, 9 and 12 months after last treatment in Treatment Group, and at screening, baseline, 3 and 6 months after randomization, as well as 3, 6, 9 and 12 months after last treatment in Control Group.

CCI

Evaluation of safety

Information regarding AEs will be collected continuously during the study. CCI

CCI

| | | |
|--|--|---------------------------|
|  GALDERMA | Title 43CH1627 Clinical Study Protocol | Doc id MA-34970 |
|--|--|---------------------------|

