4.3 Duration of Subject Participation

The total duration for each subject will be approximately 14 months for Treatment Group, 20 months for Control Group.

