8.4.3 Recording Instructions

AE will begin to be collected after ICF signed. Each subject will be questioned about AEs at each clinical visit following the screening visit. The question asked will be "Since your last clinical visit have you had any health problems?" Information on AEs can also be obtained from signs and symptoms detected during each examination or from a laboratory test, observations by the study personnel, **CCI** [REDACTED] spontaneous reports from the subjects.

When an AE is related to a device deficiency (refer to section 8.5), including technical device malfunction, the AE shall be recorded on the AE module in the eCRF and the technical complaint shall be reported separately on the clinical study complaint form.

Investigators, or other study personnel, will record all AEs in the eCRF, including:

| | | |
|--|--|---------------------------|
|  GALDERMA | Title 43CH1627 Clinical Study Protocol | Doc id MA-34970 |
|--|--|---------------------------|

2018-01-15 10:39

Effective date:

- Event term (recorded in standard medical terminology and avoiding abbreviations),
- Description of event and affected area (if applicable),
- Start date (First day with symptoms)
- Stop date (Last day with symptoms)
- Intensity (mild, moderate or severe according to definition in section 8.4.3.1)
- Seriousness (serious or not serious, according to definition in section 8.4.2)
- Causal relationship to study product and study product injection procedure (yes or no)
- Action taken (none, medication treatment, non-pharmacological treatment or other procedures/ tests, subject withdrawn)
- Outcome of the AE (ongoing, recovered, recovered with sequelae, death, chronic/ stable, not recovered at study end)

The AE module in the eCRF must be signed and dated by the Investigator.

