8.4.4 Reporting of Adverse Events

AE reporting on each subject will start after the ICF has been signed. The reporting will continue during each follow-up visit (including telephone contacts and extra visits between planned visits) until the last scheduled visit in the study.

All AEs, non-serious as well as serious, are to be reported as an AE in the eCRF.

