10.5 Safety Analysis

CCI

A graph will be generated to illustrate the incidence over time. Number of days with the event will be summarized using mean, SD, min, max and median.

All AEs will be coded by preferred terms in the MedDRA dictionary.

Related AEs will be summarised by SOC, PT and intensity. In addition, for related AEs the number of days to onset and the duration of event will be summarised by SOC and PT and treatment using mean, SD, min, max and median.

Serious AEs will be listed.

Non-related AEs will be summarised by SOC, PT, and intensity and by treatment.

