2.5.2 Adverse events

All AEs will be coded according to MedDRA. All AE summaries below will be presented by treatment.

An overall summary of AEs will be presented. The summary will include the total number of events, frequency counts and percentages of subjects with

- Any AEs and SAEs reported
- Any AEs and SAEs related to product and/or injection procedure
- Unrelated AEs and SAEs
- No AEs reported

Summaries of related AEs after each treatment occasion (including the total number of events, number and percentage of subjects) will be displayed by system organ class (SOC), preferred term

	Title Statistical Analysis Plan 43CH1627 - Chin	Doc id MA-38115
--	---	---------------------------

Effective date: 2018-08-23 03:02

Effective

Version: 1.0

(PT) and intensity. The duration and number of days to onset of related AEs will be summarized by SOC and PT using mean, SD, minimum, maximum, and median statistics.

Time to onset of an AE will be derived as the start date minus the date of most recent treatment. If the start date is missing, it will be assumed that the AE started on the day of most recent treatment.

Duration of an AE will be derived as the stop date minus the start date + 1. If the start date is missing, it will be assumed that the AE started on the day of most recent treatment. Missing stop date will not be imputed and therefore no duration will be calculated in these cases. Instead, the number of AEs that were ongoing at the end of the study will be given.

CCI

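### The AE tables set about 6 months of untreated follow-up beside 12 to 13 months of treated follow-up as crude percentages, and no visible table compares the randomized groups over a common period.

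*SAP*

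**What the plan says.** The protocol's objective (3.1) is "To evaluate the effectiveness and safety of Restylane Defyne versus a no-treatment control in the treatment of Chin Retrusion". Under protocol 4.1, "At month 6 visit after randomization, subjects in Control Group will be offered a treatment", with an optional touch-up afterwards. Both groups are then followed to 12 months after their last treatment. Protocol 4.3 gives the resulting lengths: "The total duration for each subject will be approximately 14 months for Treatment Group, 20 months for Control Group".

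SAP 2.5.2 states that "All AE summaries below will be presented by treatment". It gives no cut at Month 6, no common window and no person-time.

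Table A 41 has two columns, one for no treatment at baseline and one for treatment with Restylane Defyne. Its note defines only the treated column: Treatment Group data after the initial injection, "as well as data from subjects in the Control group after their initial treatment at Month 6 after randomization". Percentages are 100 × n/N. Table A 42 has the same two columns.

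Table A 46, for unrelated AEs, takes its layout from Table A 43, which has a single treated column. Protocol 10.5 says otherwise: "Non-related AEs will be summarised by SOC, PT, and intensity and by treatment". SAP 2.8 declares no changes from the protocol.

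**The concern.** A crude percentage of subjects with at least one event grows with the time they are watched. If one column covers about twice the follow-up of the other, the longer one shows more AEs even when the product does nothing. The any-AE, unrelated and serious rows are the ones exposed, because background illness accrues with time. They are also where a reader would look for a comparison with no treatment.

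The untreated column is not defined either. For AEs, "AE reporting on each subject will start after the ICF has been signed", which can be up to 21 days before baseline. Events before baseline cannot enter the treated column, but the SAP does not say whether they enter the untreated one. Treatment at Month 6 is only offered, and the SAP does not say how later time in Controls who decline is counted. Two programmers could produce different tables from the same data.

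No visible AE table compares the two randomized groups over the period when one is treated and the other is not. Some safety tables are redacted, so this can be said only of what is visible.

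**Working it through.** **Inputs**

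- Screening: up to 21 days (protocol 4.1).
- Untreated Control period: to the Month 6 visit (protocol 4.1 and the Control schedule in 4.7).
- Touch-up: optional, 4 weeks (28 days) after the initial treatment (protocol 4.1).
- End of follow-up: 12 months after last treatment (schedules in protocol 4.7).
- Randomized: 111 and 37 (SAP 2.7).
- One month is taken as 30.44 days.

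**Reproducing the plan's own durations**

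- Treatment Group: 21 days + 28 days + 12 months = 13.6 months, against a stated 14.
- Control Group: 21 days + 6 months + 28 days + 12 months = 19.6 months, against a stated 20.

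The schedule components therefore agree with protocol 4.3.

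**Follow-up per subject in each column**

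- Untreated: about 6 months (5.8 to 6.2 with the visit window), if the column runs from randomization to Month 6.
- Treated: 12.0 months without touch-up; 12 + 28/30.44 = 12.9 with it.
- Ratio: 12.0/6 = 2.0 to 12.92/6 = 2.15.

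**Planned subject-months, no dropout**

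- Untreated: 37 × 6 = 222.
- Treated, no Control accepts: 111 × 12 = 1,332 to 111 × 12.92 = 1,434.
- Treated, all 37 accept: 148 × 12 = 1,776 to 148 × 12.92 = 1,912. In that case 37/148 = 25% of the treated column's subjects also stand in the untreated column.

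**What the percentages would show with no product effect**

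Assume the same constant rate in both columns, no treatment effect and no dropout. With 6-month incidence p6, the monthly rate is r = −ln(1 − p6)/6, and the percentage after m months is 1 − exp(−r·m). For p6 = 10%, r = 0.0176; at 12 months the percentage is 1 − 0.9² = 19.0%, and at 12.92 months it is 20.3%.

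| Untreated, 6 months | Treated, 12.0 to 12.9 months | Ratio |
|---|---|---|
| 5% | 9.8-10.5% | 1.95-2.09 |
| 10% | 19.0-20.3% | 1.90-2.03 |
| 20% | 36.0-38.2% | 1.80-1.91 |
| 40% | 64.0-66.7% | 1.60-1.67 |
| 60% | 84.0-86.1% | 1.40-1.43 |
| 80% | 96.0-96.9% | 1.20-1.21 |

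**Variant: screening AEs counted as untreated.** With the full 21 days, untreated time is 6 + 21/30.44 = 6.69 months. The ratio becomes 1.71-1.83 in the 10% row, 1.63-1.73 in the 20% row and 1.15-1.16 in the 80% row. This is the largest such correction, since screening and baseline may be a single visit.

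**Common window.** Over the first 6 months after randomization both groups have about 6 months per subject (111 against 37), and under the same assumptions the expected percentages are equal.

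**The case against.** The strongest reply has five parts.

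- **The plan's main safety interest is largely untouched.** SAP 1.6 defines the safety endpoint as related AEs. Protocol 8.4.8 expects injection reactions to start on the treatment day and resolve within a week. This is right for related reactions. However, protocol 3.2.3 and SAP 1.2.3 cover AEs generally, and A 41 and A 42 report all of them side by side.
- **The layout is a declared choice.** The Safety population is analysed as treated, the A 41 note discloses the pooling, and neither document promises a common-period comparison by randomized group. This stands: A 41 and A 42 do not breach the rule to present by treatment. It does not make the crude comparison interpretable.
- **The analysis is descriptive and the distortion runs against the product.** Both points are true. No test or success rule is affected.
- **The ratios lean high.** Dropout (15% is planned for) and differences between subjects in proneness to events would lower them. With an assumed gamma frailty of variance 1, the 12-month ratio is 1.82 rather than 1.90 in the 10% row, 1.67 rather than 1.80 in the 20% row and 1.11 rather than 1.20 in the 80% row. Chance is also large with 37 controls: 4/37 (10.8%) has an exact 95% interval of 3.0% to 25.4%. The size is therefore uncertain; the direction is not.
- **Table A 46 loses little.** A 41 already counts unrelated AEs in both columns, and A 42 lists all AEs with an untreated column. An AE before any injection could hardly be attributed to the product or its injection. That is fair, and it makes A 46 a smaller matter. Its one-column shell still conflicts with protocol 10.5 and SAP 2.5.2.

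Redaction remains a limit. A common-period table could stand among the hidden ones, but that would settle neither the undefined untreated column nor the layout of A 46.

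**Conclusion.** The concern holds. In the visible AE comparison with no treatment, the treated column carries 2.0 to 2.15 times the follow-up per subject. Under a constant background rate with no dropout and no product effect, this alone would multiply the crude percentage by about 1.9 to 2.0 when the untreated figure is 10%, and by about 1.2 when it is 80%. The ratios are lower if screening AEs count as untreated, if proneness varies or if subjects drop out. The background rates are assumed, and the 6-month end of the untreated column is inferred from the schedule because the tables do not state it.

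The consequence is a misleading descriptive comparison in the any-AE, unrelated and serious rows. The primary analysis is unaffected. The change should be made because it is cheap and bears directly on the safety objective; the trial's main conclusion does not depend on it.

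**What to change.** 1. For the content of A 41, A 42 and A 46, add a display of AEs in the first 6 months after randomization, by randomized group, before any Control injection.
2. State when the untreated column starts and ends, including where AEs before baseline go and how Controls who decline treatment are counted.
3. Give Table A 46 its no-treatment column, as protocol 10.5 requires.
4. Keep the pooled full-period tables, but show subject-months for each column. Events per 100 subject-months may be added as a supplement, mainly for unrelated AEs, with a note that such rates dilute reactions clustered just after injection. For example, an assumed 50 first-week events per 100 subjects reads as 50/6 = 8.3 per 100 subject-months over 6 months, but 50/12.92 = 3.9 to 50/12 = 4.2 over 12 to 12.9 months.

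The cost is SAP wording and one or two extra tables. AE start dates (protocol 8.4.3) and administration dates (protocol 6.6.5) are already recorded in the eCRF, so no new data are needed.

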**Table A 42. All AEs by MedDRA System Organ Class, Preferred Term and intensity (Safety)**

		No treatment at baseline N=xx		Treatment with Restylane Defyne N=xx	
		Events	Subjects	Events #	Subjects n (%)
Primary System Organ Class Preferred Term	Intensity	Events	Subjects	Events #	Subjects n (%)
Any AE	Total	xx	xx (xx.x)	xx	xx (xx.x)
	Mild	xx	xx (xx.x)	xx	xx (xx.x)
	Moderate	xx	xx (xx.x)	xx	xx (xx.x)
	Severe	xx	xx (xx.x)	xx	xx (xx.x)
SOC1	Total	xx	xx (xx.x)	xx	xx (xx.x)
	Mild	xx	xx (xx.x)	xx	xx (xx.x)
	Moderate	xx	xx (xx.x)	xx	xx (xx.x)
	Severe	xx	xx (xx.x)	xx	xx (xx.x)
PT11	Total	xx	xx (xx.x)	xx	xx (xx.x)
	Mild	xx	xx (xx.x)	xx	xx (xx.x)
	Moderate	xx	xx (xx.x)	xx	xx (xx.x)
	Severe	xx	xx (xx.x)	xx	xx (xx.x)

Table A 43. Related AEs by MedDRA System Organ Class, Preferred Term and intensity (Safety)

		Treatment with Restylane Defyne N=xx	
Primary System Organ Class Preferred Term	Intensity	Events #	Subjects n (%)
Any related AE	Total	xx	xx (xx.x)
	Mild	xx	xx (xx.x)
	Moderate	xx	xx (xx.x)
	Severe	xx	xx (xx.x)
SOC1	Total	xx	xx (xx.x)
	Mild	xx	xx (xx.x)
	Moderate	xx	xx (xx.x)
	Severe	xx	xx (xx.x)
PT11	Total	xx	xx (xx.x)
	Mild	xx	xx (xx.x)
	Moderate	xx	xx (xx.x)
	Severe	xx	xx (xx.x)

Note: Treatment with Restylane Defyne columns include data from subjects in the Restylane Defyne group after their initial treatment at baseline, as well as data from subjects in the Control group after their initial treatment at Month 6 after randomization

Note: At each level of summarization subjects are counted once

% = 100*n/N

Table A 44. Duration (days) of related AEs by MedDRA System Organ Class and Preferred Term (safety)

	Treatment with Restylane Defyne N=xx						
	Ongoing	n	mean	SD	min	Median	Max
Any related AE							
SOC1							
PT11							
PT12							

Note: Treatment with Restylane Defyne columns include data from subjects in the Restylane Defyne group after their initial treatment at baseline, as well as data from subjects in the Control group after their initial treatment at Month 6 after randomization

Table A 45. Time to onset (days) of related AEs, by MedDRA System Organ Class and Preferred Term (Safety)

As Table A 44.

Note: Treatment with Restylane Defyne columns include data from subjects in the Restylane Defyne group after their initial treatment at baseline, as well as data from subjects in the Control group after their initial treatment at Month 6 after randomization

Table A 46. Unrelated AEs by MedDRA System Organ Class, Preferred Term and intensity (Safety)

As Table A 43.

Note: Treatment with Restylane Defyne columns include data from subjects in the Restylane Defyne group after their initial treatment at baseline, as well as data from subjects in the Control group after their initial treatment at Month 6 after randomization

**Table A 47. Action taken due to related AEs by MedDRA System Organ Class and Preferred Term (Safety)**

System Organ Class Preferred Term	Action taken			
	Treatment with Restylane-Defyne N=xx			
	None	Medication treatment	Non-pharmacological treatment or other procedures/tests	Subject withdrawn
SOC				
PT1				
PT2				
...				
All				

Note: Treatment with Restylane Defyne columns include data from subjects in the Restylane Defyne group after their initial treatment at baseline, as well as data from subjects in the Control group after their initial treatment at Month 6 after randomization

Title

Statistical Analysis Plan 43CH1627 - Chin

Doc id

MA-38115

CCI

Title

Statistical Analysis Plan 43CH1627 - Chin

Doc id

MA-38115

CCI

Title

Statistical Analysis Plan 43CH1627 - Chin

Doc id

MA-38115

CCI

Page 41 of 41

Version: 1.0

Effective

Effective date: 2018-08-23 03:02

 GALDERMA	<small>Title</small> Statistical Analysis Plan 43CH1627 - Chin	<small>Doc id</small> MA-38115
--	--	--

2018-08-23 03:02

Effective date:

Effective

Version: 1.0

SIGNATURES PAGE

Date	Signed by
2018-08-22 11:44	PPD 
Justification	Approved by Owner
2018-08-22 11:47	PPD 
Justification	Approved by Technical Expert
2018-08-22 14:44	PPD 
Justification	Approved by Technical Expert
2018-08-23 03:02	PPD 
Justification	Approved by Project Manager
